9.2.2 Prohibited medication and surgery phase II

No simultaneous systemic anti-cancer therapy is permitted while on study, however local radiotherapy is allowed at any time provided at least one non-irradiated tumor site is available for evaluation. Patients may undergo surgery to any site prior to first extent of disease evaluation provided there another site of evaluable disease remains; patients may be rendered NED by surgery after their first EOD evaluation.

All interventions below are common to both phase I and phase II

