2.1.2. Phase II

After RP2D is determined, a phase II trial will be carried out to assess the anti-tumor activity of hu3F8-BsAb. Two groups of patients will be studied: Group 1 will consist of patients with relapsed or refractory NB and Group 2 of relapsed or refractory measurable osteosarcoma. Hu3F8-BsAb is given on Days 1 and 8 of each cycle. The duration of each cycle is 28 days. However, cycles may be delayed for up to 56 days if >grade 2 toxicity is encountered.

HAHA titer will be measured after each cycle. If HAHA develops, cycles are deferred for up to 120 days until HAHA titer <1300 U/ml. Extent of Disease Evaluation (EOD) will be performed after the second dose of cycle 2 and cycle 4, then every 3 months thereafter.

A total of 4 cycles will be given, and patients with no life-threatening toxicity clearly attributable to hu3F8-BsAb, no progressive disease, continuing to meet all eligibility criteria and HAHA titer is <1300U/ml have the option of receiving additional cycles up to 2 years from the start of the Hu3F8-BsAb treatment. Patients may continue therapy beyond 4 cycles even if they achieve remission.

After cycle 4, duration between cycles can range from 28-120 days. Patients will undergo physical examination, Complete Blood Count (CBC) and complete chemistry and immune correlates will be tested as described in Protocol Section 10.

For Group 1, the overall response rate will be evaluated and is defined as the proportion of patients achieving Complete Remission (CR) or Partial Response (PR) based on revised International Neuroblastoma Response Criteria (INRC)³ as the best of the responses at the end of cycle 2 and cycle 4. (See Section 2.4.2.1) excluding potential response assessments after initiation of any new prohibited anticancer treatment).

For Group 2, 4-month Progression Free Survival (PFS) will be assessed and is defined as the proportion of patients who have not developed progressive disease nor died at the end of 4 months from the first dose of Hu3F8-BsAb. In addition, number of patients who have CR or PR as the best of the responses at the end of cycle 2 and cycle 4 will be determined. (see Section 2.5.2.2)

Hu3F8-BsAb is given IV over ~1-3 hours on Days 1 and 8 for each cycle.

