2.4.2. Phase II

2.4.2.1. ORR For Group 1 (relapsed or refractory NB)

For relapsed or refractory NB patients, the primary endpoint will be the ORR defined as the proportion of patients achieving CR or PR based on INRC as the best response at the end of cycle 4.

For this analysis, Best Overall Response (BOR) will be derived as the best response at the end of cycle 4, excluding any potential response assessments after initiation of any new prohibited anticancer treatment.

Overall response will be defined by the investigator in the Response Summary eCRF form by combining response of the individual components (i.e. soft tissue, bone, and bone marrow disease):

- Complete Response/Remission (CR): All components meet criteria for CR.

- Partial Response/Remission (PR): PR in at least one component and all other components are either CR, Minimal Disease (MD) (bone marrow), PR (soft tissue or bone), or Not Involved (NI)*; no component with progression disease.
- Mixed Response (MR): PR or CR in at least one component but at least one other component with Stable Disease; no component with PD.
- Stable Disease: Stable Disease in one component with no better than Stable Disease or NI* in any other component; no component with progressive disease.
- Progressive Disease: Any component with Progressive Disease.
 *NI Site not involved at trial entry and remains uninvolved.

Mixed Response corresponds to Minor Response in the *Revisions to the International Neuroblastoma Response Criteria: A Consensus Statement From the National Cancer Institute*³. Thus it will be considered as Minor Response for the analyses.

Primary (soft tissue) Tumor Response:

- CR: <10mm residual soft tissue at primary site AND Complete resolution of MIBG or Fluorine-18-Fluorodeoxyglucose Positron Emission Tomography (FDG-PET) uptake (for MIBG-nonavid tumors) at primary site.
- PR: ≥30% decrease in longest diameter of primary site AND MIBG or FDG-PET uptake at primary site stable, improved, or resolved.
- Progressive Disease: >20% increase in longest diameter taking as reference the smallest sum on trial (this includes the baseline sum if that is the smallest on trial) AND Minimum absolute increase of 5mm in longest dimension.
- Stable Disease: Neither sufficient shrinkage for PR or sufficient increase for PD at the primary site.

Tumor Response at Metastatic Soft Tissue and Bone Sites:

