2.5.2. Phase II

2.5.2.1. Duration of Complete Remission

Duration of CR is defined only for patients who achieve CR after hu3F8-BsAb and will be calculated from the time of remission to the date of progression or death, whichever occurs first.

Same censoring rules as for PFS will be applied for CR duration analysis (See section 2.4.2.2).

CR duration (in months) will be computed as [date of progression or death or censoring – CR date + 1]/30.4375.

CR duration will be calculated with one decimal.

2.5.2.2. ORR for Group 2

ORR will be defined as the proportion of patients achieving CR or PR based on RECIST v1.1 as the best response at the end of cycle 4 (excluding potential response assessments after initiation of any new prohibited anticancer treatment).

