6.6.1. Primary Efficacy Analysis for Phase II

6.6.1.1. ORR for Group 1

The primary efficacy variable of relapsed or refractory NB patients of phase II is defined as ORR at the end of cycle 4 excluding potential response assessments after initiation of any new prohibited anticancer treatment.

The null hypothesis is that the hu3F8-BsAb treatment has ORR < 25%. The alternative hypothesis is that the ORR after the hu3F8-BsAb treatment is \geq 25%.

90% and 95% two-sided confidence intervals for ORR will be computed using Wilson's method. If the two-sided 90% confidence interval does not include the null ORR rate of 25% the treatment will be considered as successful.

Patients in the FAS will be included into the assessment even if they are removed from the trial before completing cycle 4 due to any reasons.

The number and percentage of responder patients (Yes/ No) with details by best response categories (CR, PR and MR versus Stable Disease, Progressive Disease, Not Evaluable, Missing) will be described in the FAS and the confidence interval using the Wilson's method will be provided.

In addition, overall responses at each cycle will excluding potential response assessments after initiation of any new prohibited anticancer treatment be provided with the 90% and 95% confidence intervals using the Wilson's method.

Patients whose CRF response is "Very Good Partial Response" will be considered as "Partial Response" for the analyses.

ORR values will be also presented in a data listing as well as overall responses at each cycle.

6.6.1.2. 4-month PFS for Group 2

The primary efficacy variable of relapsed or refractory osteosarcoma patients of phase II is defined as 4-month PFS.

The null hypothesis is that the hu3F8-BsAb treatment has 4-month PFS <12%. The alternative

hypothesis is that the 4-month PFS after hu3F8-BsAb treatment is $\geq 12\%$.

The Kaplan-Meier estimate of the median time will be provided with 25th percentile and 75th percentile as well as PFS rates at 4 months with corresponding 90% and 95% Confidence Intervals.

In addition, the results will be presented graphically in Kaplan-Meier plots including count for numbers of patients at risk.

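### In phase II, a CR or PR first reached through permitted surgery to no evidence of disease can count as a response in the Group 1 primary ORR

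*Protocol*

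**What the plan says.** **Local therapy permitted in phase II (Protocol 9.2.2).** Only simultaneous systemic anticancer therapy is barred. Three permissions follow:
- Before the first evaluation: "Patients may undergo surgery to any site prior to first extent of disease evaluation provided there another site of evaluable disease remains".
- After it: "patients may be rendered NED by surgery after their first EOD evaluation". This permission has no condition about remaining disease.
- Radiotherapy: "local radiotherapy is allowed at any time provided at least one non-irradiated tumor site is available for evaluation".

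**Timing (Protocol 9.2.1).** Disease is evaluated after the second dose of cycle 2 and again after the second dose of cycle 4.

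**What is left out of best response.** SAP 2.4.2.1 derives best overall response for Group 1 "excluding any potential response assessments after initiation of any new prohibited anticancer treatment". SAP 6.6.1.1 repeats this for the primary analysis: "ORR at the end of cycle 4 excluding potential response assessments after initiation of any new prohibited anticancer treatment". SAP 2.1.2 and 2.5.2.2 (Group 2 ORR) use the same filter, and so do the ORR sensitivity analyses in 6.6.2 and 6.6.4.

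**How response is scored.** Protocol 12.3 and SAP 2.4.2.1 score neuroblastoma by lesion size, MIBG or FDG-PET uptake and marrow infiltration. Protocol 12.4.2 scores other tumors by target-lesion diameters and new sites. Neither text mentions resected lesions. For neuroblastoma, "Overall response will be defined by the investigator in the Response Summary eCRF form".

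**Duration of CR (SAP 2.5.2.1).** "Duration of CR is defined only for patients who achieve CR after hu3F8-BsAb". Nothing says how that CR must have been reached.

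**The concern.** Surgery allowed by Protocol 9.2.2 is not prohibited treatment, so the SAP's only exclusion does not reach it. A patient who is stable on drug at cycle 2 and then has all disease removed can be scored CR at cycle 4 without any drug effect.

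Group 1 success is judged against a fixed historical 25% with no control arm, so nothing offsets responses produced by surgery. Each one counted brings the total closer to the success threshold. The Group 2 ORR has no hypothesis or decision rule (Protocol 14.2.2.2). There the effect is limited to a descriptive comparison with history and to who enters the duration-of-CR analysis.

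The planned outputs would not show how often this happened. Surgery is not reported as an adverse event (Protocol 17.2.1), SAP 6.4.4 summarises medications only, and no table of on-study surgery or radiotherapy is planned. SAP 3 defines no estimand, and SAP 6.6.2.3 marks analyses of intercurrent events as not applicable.

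**Working it through.** **1. Can the written criteria score a surgical CR in neuroblastoma?** Take a hypothetical patient whose only disease is a 30 mm primary, with clear marrow and no metastases.
- Entry: Protocol 6.1.2 accepts imaging-evident disease or marrow disease, so the patient is eligible.
- Cycle 2: the lesion is unchanged, so response is stable disease. The patient has no progression and continues.
- Between the evaluations: complete resection, as 9.2.2 permits.
- Cycle 4: the primary site has less than 10 mm residual and no uptake, which is CR (12.3.2). Marrow without tumor is CR whatever the baseline (12.3.4). With every component at CR, overall response is CR (12.3.1).

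No step requires shrinkage on drug, and the SAP filter does not remove the cycle 4 assessment.

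**2. Reproduce the plan's own figure.** Inputs from Protocol 14.2.1.1 and SAP 6.6.1.1: n = 30, null 25%, alternative 50%, one-sided 95% Wilson limit (z = 1.645), stated power 90%.

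Wilson lower limit = [p + z²/2n − z√(p(1−p)/n + z²/4n²)] / (1 + z²/n)
- 12/30: (0.4000 + 0.0451 − 0.1539) / 1.0902 = 0.267, above 0.25: success.
- 11/30: (0.3667 + 0.0451 − 0.1516) / 1.0902 = 0.239: not success.

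Success therefore needs at least 12 responders. Exact power P(Bin(30, 0.50) ≥ 12) = 0.8998, which matches the stated 90%. Exact type I error P(Bin(30, 0.25) ≥ 12) = 0.0507.

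**3. Effect of k surgical responders.** The documents do not give k, so 0 to 3 is an assumed range. All k patients are scored as responders and the drug rate p applies to the other 30 − k.

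Current rule: P(success) = P(Bin(30−k, p) ≥ 12−k)

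**4. Effect of the proposed rule.** All k patients are scored as non-responders. For power this is the worst case, because some of them could already have responded before surgery.

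Proposed rule: P(success) = P(Bin(30−k, p) ≥ 12)

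| k | Current rule, p = 0.25 | Current rule, p = 0.20 | Proposed rule, p = 0.25 | Proposed rule, p = 0.50 (power) |
|---|---|---|---|---|
| 0 | 0.051 | 0.009 | 0.051 | 0.900 |
| 1 | 0.086 | 0.020 | 0.039 | 0.868 |
| 2 | 0.138 | 0.039 | 0.029 | 0.828 |
| 3 | 0.214 | 0.074 | 0.022 | 0.779 |

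**The case against.** **The route is narrow.** Progression at any time is a response failure (Protocol 12.2), and every involved neuroblastoma component must qualify. Marrow disease cannot be resected. A stable component alongside a resected one gives mixed response, which is outside CR/PR. This stands: the clear case is resectable disease with no persisting marrow or unresected disease.

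**Radiotherapy and early surgery have provisos.** Protocol 9.2.2 requires a non-irradiated site, or another evaluable site, to remain. A reader might infer that any permitted local therapy inflates ORR in the same way. The documents do not support that: the provisos suggest that response is to be read on remaining disease, and a stable untreated component blocks PR. These cases are weaker, though no text restricts scoring to untreated sites.

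**The cited criteria may settle it.** Response follows the revised INRC and RECIST 1.1, whose full texts are not in the documents. The SAP names protocol A(8) as its source, while 9.2.2 is read here from A(10). Both limits stand. If the criteria do contain a rule, stating it in the SAP costs little.

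**Other outputs help.** Per-cycle response tables (SAP 6.6.1.1, 6.6.3.5) give a cycle 2 rate that precedes surgery to NED, and scan data are listed (SAP 6.6). This is useful context, but it does not change the success rule or identify who was operated on.

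**Censoring may already act on duration of CR.** It borrows the PFS rules, which censor at new anticancer treatment whether or not prohibited (SAP 2.4.2.2). The SAP does not say whether surgery is such a treatment. In any case, censoring does not decide whether a surgical CR enters the analysis. A reader might extend the point to the Group 2 primary PFS; given that broader censoring wording, this is not claimed here.

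**Conclusion.** The point holds for surgery to NED between the first evaluation and the cycle 4 assessment. As written, the plan can count a CR or PR first reached through that surgery as a response in the Group 1 primary ORR, in the Group 2 ORR, and as the CR that starts duration of CR.

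If one of 30 patients were converted, false success at a true ORR of 25% would rise from 0.051 to 0.086; with three it would be 0.214. A reader might take these as the trial's actual error rates. They are not: they illustrate an assumed k, and the documents give no surgery rate. At a true ORR of 20%, two such patients leave false success at 0.039, below 5%, and three give 0.074.

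The conclusion rests on the criteria as they appear in the protocol and SAP, and on reading prohibited against the current 9.2.2. Confidence is moderate. The rule should be settled before phase II responses are seen, because one or two patients could decide a result near 12/30.

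**What to change.** Change the analysis only; the clinical permission in 9.2.2 is not at issue.

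1. In SAP 2.1.2, 2.4.2.1, 2.5.2.2, 6.6.1.1, 6.6.2, 6.6.3.5 and 6.6.4, keep the existing exclusion and add: *After surgery that leaves no evaluable disease, best response is the best documented before that surgery; a CR or PR first documented after it is not counted as a response.*
2. In SAP 2.5.2.1 add: *A CR first documented after such surgery does not start duration of CR.*
3. In SAP 6.6.2 and 6.6.4 add: ORR under the current rule, with local therapy ignored; ORR using only assessments before any on-study surgery or radiotherapy; and the number of patients, by group, with surgery or radiotherapy before the cycle 4 assessment.
4. Apply the same wording to DCR (2.6.2.4) and to the phase I ORR (2.5.1.3, 6.6.3.1), so that the SAP has one best-response rule.

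Removing treated lesions from the baseline and follow-up sums is a tempting addition but is not advised. It does not cover the MIBG score, PET-avid lesion counts or marrow, and it can itself create a PR. Under Protocol 12.4.2, take target lesions of 30 + 20 + 20 mm, with the unresponsive 30 mm lesion resected and the others shrinking to 14 mm each. The sum goes from 40 to 28 mm (−30%, PR). Without surgery it would go from 70 to 58 mm (−17%, stable disease). Surgery that leaves disease, and radiotherapy, are better examined through the second sensitivity analysis in item 3.

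**Cost.** A drug response that would have appeared only after NED surgery is not counted, so ORR is conservative. Worst-case power at 50% is 0.868, 0.828 or 0.779 with one, two or three such patients. False success under this rule is at most 0.051. Dates and sites of on-study surgery and radiotherapy must be in the dataset. The eCRF is not in the documents, so whether they are captured is unknown.

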9.3 HAHA testing

Blood (~5ml per draw) drawn before each cycle for HAHA testing will be measured using ELISA. Antiidiotype antibodies (Ab3, Ab3') will be also tested with the same blood samples.⁸¹

This blood sample may also be tested for HAMA. HAMA positivity is allowed and will not affect patients' eligibility for treatment.

9.4 Immunological effects of hu3F8-BsAb

Lymphocyte subsets (including CD3, CD4, CD8, Foxp3, CD127, CD45RA, CCR7) and T cell activation/exhaustion markers (including CD25, PD-1) will be tested before and after the hu3F8-BsAb treatment (See Section 10). Each draw will collect about 16 mL of serum. Analysis will be performed in the MSK Immune Monitoring Core Facility. CBC should be checked with blood collected on the same day. Cytokine levels (including IFN-y, IL-6, IL-8, IL-10) will be measured before and after the hu3F8-BsAb treatment during cycle 1 of phase I, and analyzed in the MSK Immune Monitoring Core Facility. During subsequent cycles of phase I or in phase II, these cytokine levels will be measured if CRS is clinically suspected. Each draw for cytokine levels will collect about 4mL of serum.

9.5 Bone marrow (BM) RNA

For NB patients, tumor RNA will be used for transcriptome and microRNA profiling. Tumor RNA in BM from blood will be used for minimal residual disease (MRD) testing, to be completed in the [name] Lab at MSK. The samples will not have any associated patient-specific identifying information, but will be linked to clinical information such as patient age, gender, tumor stage, tumor recurrence status,

and tumor site. Frozen tumors will be tested for tissue antigens and gangliosides (including but not limited to GM2, GD2, GD3].

9.6 Stool microbiome

Based on emerging data on the impact of stool microbiome on function of immunotherapeutic agents, a stool sample will be collected on all patients prior to first dose of hu3F8-BsAb, where feasible. Sequencing of stool microbiota will be performed and correlated with clinical and immunological response.

10 EVALUATION DURING TREATMENT/INTERVENTION

10.1 History and physical exam

- Phase I cycle 1: History and physical exams will be completed every day for the first 4 days, on Day 8, and weekly thereafter until Day 28.
- For subsequent cycles in Phase I, and Phase II: Before each dose of hu3F8-BsAb and within 72 hours of treatment.
- **10.2** Patients are monitored by pulse oximeter during hu3F8-BsAb infusion and have blood pressure taken no later than 30 minutes after the end of infusion of hu3F8-BsAb. In cycle 1 and for all inpatient treatment, blood pressure measurement (standing, sitting and lying down) will be taken pre infusion, once daily throughout their hospital stay and at discharge. For treatment administered outpatient, blood pressure measurement (standing, sitting and lying down) will be taken pre infusion and at discharge.
- 10.3 CBC
 - Phase I cycle 1: CBC will be done approximately on Days 2, 5, 8 (prior to the second dose of hu3F8-BsAb), and approximately Days 15 and 28.
 - For subsequent cycles in Phase I, and Phase II: Before each dose of hu3F8-BsAb. (Pre-treatment CBC can be used for pre-cycle 1 CBC.)

10.4 C3 and CH50

• Phase I only: C3 and CH50 will be tested on Day 2 during cycle 1.

10.5 Urinalysis

- Phase I only: In cycle 1, urinalysis will be tested prior to each dose of hu3F8-BsAb and approximately one week after the second dose. (Pre-treatment urinalysis can be used for pre-cycle1 test.)
- **10.6** Liver and kidney function blood tests (ALT, AST, alkaline phosphatase, albumin, bilirubin, BUN and creatinine), and serum electrolytes (sodium, potassium, chloride, bicarbonate, magnesium, and phosphate).

- Phase I cycle 1: Before each dose of hu3F8-BsAb, within 72 hours after each dose of hu3F8-BsAb, and on approximately Day 15. (Pre-treatment test can be used for pre-cycle1 test.)
- For subsequent cycles in Phase I, and Phase II: Before each dose of hu3F8-BsAb. (Pre-treatment test can be used for pre-cycle1 test.)
- **10.7** Pregnancy test within 2 weeks before each cycle, if applicable.
- **10.8** Phase I only: Electrocardiogram will be done post the first infusion of hu3F8-BsAb on Day 1 and prior to the second dose hu3F8-BsAb on Day 8 during cycle 1. This must be done on the same day as the dose, but does not need to be immediately post or immediately prior.
- **10.9** Phase I only: Pharmacokinetic studies will be done as described in Section 9.1.4
- **10.10** Phase I and II: Cmax and Ctrough will be measured as described in Section 9.1.4
- **10.11** Ferritin and C-reactive protein
 - Phase I cycle 1: On Day 8 (prior to the second dose of hu3F8-BsAb) and approximately on Day 28.
 - For subsequent cycles in phase I, and phase II: If CRS is suspected based on clinical symptoms. (See Section 11.3)
- 10.12 LDH
 - Phase I cycle 1: On Day 8 (prior to the second dose of hu3F8-BsAb) and approximately on Day 28.
 - For subsequent cycles in phase I, and phase II: If CRS is suspected based on clinical symptoms. (See Section 11.3)
- **10.13** Blood will be obtained before each cycle of hu3F8-BsAb to assay for HAHA titers, then approximately every 3 months for 24 months from first hu3F8-BsAb dose, and then approximately every 6 months for up to 5 years from first hu3F8 dose or until patient is off study, whichever is earlier. This blood sample may also be tested for HAMA.
- **10.14** Blood will be tested for cytokine studies including IFN-y, IL-6, IL-8, IL-10.
 - Phase I cycle 1: cytokine studies should be tested prior to and ~ 6-8 hrs after the first and second infusion of hu3F8-BsAb, and on Days 2, 3, 4, 9, 10, and 11.
 - For subsequent cycles in Phase I and Phase II: If CRS is suspected based on clinical symptoms. (See Section 11.3)
- **10.15** Lymphocytes from heparinized blood will be collected for lymphocyte subset markers (including CD3, CD4, CD8, Foxp3, CD127, CD45RA, CCR7) and T cell activation/exhaustion markers (including CD25 and PD-1).

- Phase I Cycle 1: On Days 2, 8 (prior to hu3F8-BsAb), 9, 10 and 11, and approximately Days 15 and 28.
- For subsequent cycles in phase I, and phase II: Before each dose of hu3F8-BsAb.
- **10.16** For patients with a diagnosis of neuroblastoma, the following studies will be performed any time after the second dose of hu3F8-BsAb in cycle 2 and cycle 4, and then approximately every 3 months while on study:
 - BM aspirates and biopsies from bilateral iliac crests for standard histochemical studies, as well as for immunocytology and other molecular markers of disseminated NB.
 - Imaging by computed tomography (CT) or magnetic resonance imaging (MRI) of primary tumor site, plus metaiodobenzylguanidine (MIBG) scan or positron emission tomography (PET).
- **10.17** For patients with osteosarcoma or GD2(+) tumors, the following studies will be performed any time after the second dose of hu3F8-BsAb in cycle 2 and cycle 4*, and then approximately every 3 months while on study:
 - Disease evaluations with imaging by computed tomography (CT) or magnetic resonance imaging (MRI) of primary tumor site and/or known site(s) of relapse (if applicable), with/without positron emission tomography (PET) or bone scan, or other diagnostic imaging as appropriate for specific disease.

*Cycle 4 scans should occur at approximately 4 months (+/- 1 month) in order for scans to be used to evaluate the 4 month disease control rate (see section 14.2.1.2).

- 10.18 Pain Assessment (Phase I only): Pain scores will be assessed using the Face, Legs, Arms, Cry, Consolability (FLACC) scale⁸²⁻⁸⁴ and/or the numeric scale⁸⁵, as appropriate (see Appendix A for pain scales). Pain scores will be evaluated at the following time points on days with hu3F8-BsAb treatment: (a) once prior to commencement of any study drug administration, (b) at least once during the acute pain episode when rescue pain medication doses are required (for hu3F8 this is towards the end of the 30 minute infusion or soon after completion of antibody infusion) and (c) ~1 hour after the end of infusion or prior to discharge from the Pediatric Day Hospital. Pain scores will be used to establish safety for the Phase I primary objective (Section 2.1). Pain scores will be used to assist clinical judgment (e.g. decision of pain medication use, observation of pain relief) and for documentation.
- **10.19** Phase I and II: stool sample collection as described in section 9.6.

All research blood (as identified below) will be completed where feasible. Patients who are 10 kilograms or less in weight will only have research bloods drawn at the discretion of the Principal Investigator.

Tests	Pre- treatment	During Treatment	During Follow-up
Complete history and physical	V	Cycle 1: Daily from Day 1 through Day 4, on Day 8, then weekly thereafter until Day 28 Subsequent Cycles: Before each dose of hu3F8-BsAb and within 72 hours of treatment	-
Pharmacokinetic studies (research blood)	\checkmark	See Section 9.1 Cycle 1: As shown in Table 5 Subsequent Cycles: Before each dose of hu3F8-BsAb, ~5 minutes after hu3F8-BsAb infusion	
Complete blood count	~	Cycle 1: Approximately Days 2, 5, 8 (prior to the second dose of hu3F8- BsAb), and approximately Days 15 and 28. Subsequent Cycles: Before each dose of hu3F8-BsAb	_
Liver and Renal function tests (ALT, AST, alkaline phosphatase, albumin, bilirubin, BUN and creatinine) and serum electrolytes (sodium, potassium, chloride, bicarbonate, magnesium, and phosphate)	~	Cycle 1: Before each dose of hu3F8- BsAb, within 72 hours after each dose of hu3F8-BsAb and approximately Day 15 Subsequent Cycles: Before each dose of hu3F8-BsAb	_
C3 & CH50	\checkmark	Cycle 1 Only: Day 2	-
LDH	\checkmark	Cycle 1: Day 8 and approximately Day 28 Subsequent Cycles: If CRS is suspected based on clinical symptoms	
Ferritin and C-reactive protein	\checkmark	Cycle 1: Day 8 and approximately Day 28 Subsequent Cycles: If CRS is suspected based on clinical symptoms	_
SpO2 and Blood pressure measurement	Blood pressure measurement (standing, sitting, lying down)	SpO2: During hu3F8-BsAb BP: No later than 30 minutes after the end of hu3F8-BsAb infusion Cycle 1: Blood pressure measurement (standing, sitting, lying down) pre infusion, once daily throughout hospital stay and at discharge. For outpatient treatment: pre infusion and at discharge	-

Table 6	Phase I
	I mase I

Tests	Pre- treatment	During Treatment	During Follow-up
Blood for HAHA	~	Before each cycle	Approximately q3 months for 24 months from first hu3F8- BsAb dose and then q6 months for up to 5 years from first dose or until patient is off study, whichever is earlier
Urinalysis	\checkmark	Cycle 1: Prior to each dose of hu3F8- BsAb and approximately one week after the second dose	-
Pregnancy test, if applicable	\checkmark	Within 2 weeks before each cycle	-
Electrocardiogram	\checkmark	Cycle 1: Post-infusion of the first dose and prior to the second dose on Day 8	-
ЕСНО	\checkmark	-	-
Cytokine studies (research blood)	\checkmark	Cycle 1: prior to and ~ 6-8 hrs after the first and second hu3F8-BsAb dose, and on Days 2, 3, 4, 9, 10 and 11 Subsequent Cycles: If CRS is suspected based on clinical symptoms	-
Lymphocyte subsets, T cell activation/exhaustion markers (research blood)	√	Cycle 1: on Days 2, 8 (prior to hu3F8- BsAb), 9, 10, and 11, and approximately on Days 15 and 28 Subsequent Cycles: Before each dose of hu3F8-BsAb	-
Bone marrow studies*	\checkmark	Any time after the second dose in cycle 2 and cycle 4 and approximately every 3 months thereafter	-
CT/MRI, MIBG scan* with/without PET, bone scan	\checkmark	Any time after the second dose in cycle 2 and cycle 4 and approximately every 3 months thereafter	-
Pain Assessment	V	On days of hu3F8-BsAb treatment: prior to hu3F8-BsAb administration, during acute pain episode, and ~1 hour after the end of infusion or prior to discharge from the PDH	-
Stool microbiome	✓, where feasible	-	-

*only for patients with neuroblastoma

Table 7Phase II

Tests	Pre- treatment	During Treatment	During Follow-Up
Complete history and physical	\checkmark	Before each dose of hu3F8-BsAb and within 72 hours of treatment	-
Complete blood count	\checkmark	Before each dose of hu3F8-BsAb	-

Tests	Pre- treatment	During Treatment	During Follow-Up
Liver and Renal function tests (ALT, AST, alkaline phosphatase, albumin, bilirubin, BUN and creatinine) and serum electrolytes (sodium, potassium, chloride, bicarbonate, magnesium, and phosphate)	~	Before each dose of hu3F8-BsAb	-
LDH	\checkmark	If CRS is suspected based on clinical symptoms	
Ferritin and CRP	\checkmark	If CRS is suspected based on clinical symptoms	-
SpO2 and Blood pressure measurement	Blood pressure measurement (standing, sitting, lying down)	SpO2: During hu3F8-BsAb infusion BP: No later than 30 minutes after the end of hu3F8-BsAb infusion Cycle 1: Blood pressure measurement (standing, sitting, lying down) pre infusion, once daily throughout hospital stay and at discharge. For outpatient treatment: pre infusion and at discharge	-
Blood for HAHA	√(if applicable)	Before each cycle	Approximately q3 months for 24 months and then q6 months for up to 5 years from first hu3F8 dose or until patient is off study, whichever is earlier
Pregnancy test, if applicable	\checkmark	Within 2 weeks before each cycle	-
Electrocardiogram	\checkmark	-	-
ECHO	\checkmark	-	-
Cytokine studies (research)	\checkmark	If CRS is suspected based on clinical symptoms	-
Lymphocyte subsets, T cell activation/exhaustion markers (research)		Before each dose of hu3F8-BsAb	-
Bone marrow studies*	~	After the second dose of cycle 2 and cycle 4 and approximately every 3 months thereafter	-
CT/MRI, MIBG scan* with/without PET, bone scan	\checkmark	After the second dose of cycle 2 and cycle 4 and approximately every 3 months thereafter	-
Stool microbiome	✓, where feasible	-	-

*only for patients with neuroblastoma

